4.4.3 Schedule of Assessment

Assessments	Baseline	Post Therapy	Mo 3	Mo 6	Mo 12	Mo 18	Mo 24	Mo 30	Mo 36	Mo 42	Mo 48	Mo 54	Mo 60	Extended every 6 months
			(+/-) 30 days		(+/-) 60 days									
Medical history Office visit	X		X		X		X		X		X		X	
Medical history Office visit OR phone follow-up				X		X		X		X		X		X
Review Past/Current Medications	X	X(5)	X	X	X	X	X	X	X	X	X	X	X	X
Physical Exam	X			X		X		X		X		X		
Blood Tests (INR, creatinine, hemoglobin, hematocrit)	X													
12 Lead Electrocardiogram (ECG)	X	X(5)												
Transthoracic 2-D Echocardiogram	X													
Trans-esophageal Echocardiogram (1) (2)	X													

Assessments	Baseline	Post Therapy	Mo 3	Mo 6	Mo 12	Mo 18	Mo 24	Mo 30	Mo 36	Mo 42	Mo 48	Mo 54	Mo 60	Extended every 6 months
			(+/-) 30 days		(+/-) 60 days									(+/-) 60 days
CT/MR Evaluation (1) (3)	X		X(4)											
CABANA Box/Ambulatory Monitor Symptom Event Recording		Throughout the 60 month follow-up periods when Atrial Fibrillation symptoms are present												
CABANA Box/Ambulatory Monitor 24-Hour Holter / AC;FD (monthly during Year 1)	X	Monthly / 1,2,3,4,5,7,8,9,10,11				Every 6 months / 15,21,27,33,39,45,51,57								
CABANA Box/Ambulatory Monitor 96-Hour Holter			X	X	X	X	X	X	X	X	X	X	X	
Economic and QOL Survey SF36, DASL	X		X		X		X		X		X		X	X
Economic and QOL Survey Toronto AF Severity Scale AFEQT, WPAI, Stanford Presenteeism	X			X		X		X		X		X		X
AF Severity/Symptom Check List MAFSI, EQ5D	X		X		X		X		X		X		X	X
Review Adverse Events	X	X(5)	X	X	X	X	X	X	X	X	X	X	X	X

- (1) Ablation therapy subjects;
- (2) Or as warranted throughout trial;
- (3) 150 subjects randomized to Drug Therapy;
- (4) 3 months following therapy initiation = end of blanking period. Or as indicated for PV stenosis
- (5) Hospital discharge or following Drug Therapy initiation

All procedures and laboratory tests during follow-up should be performed whether or not a subject receives treatment according to the protocol.

5.0 Treatment Arms

5.1 Description of Treatment Arms

5.1.1 Treatment Strategies

Rather than comparing a specific drug therapy against any specific ablative intervention, CABANA compares two treatment strategies. The first is that of medical therapy with the intention of controlling AF rhythm or rate. The second strategy is that of ablative intervention designed to eliminate AF. The following guidelines will shape therapy selection and implementation.

5.2 Pharmacologic Approach to AF (Drug Therapy)

It is recommended that drug treatment patients first receive rate control medication and the effect on ventricular response during the blanking period documented. Medication use must conform to the Guidelines for Management of Subjects with AF published in 2006 by the ACC/AHA/ESC [92]. Approved drugs and minimum dosing guidelines are as specified below.

5.2.1 Drugs Approved for Rate Control

Drug	Administration	Minimum recommended daily dosage
Digoxin (Lanoxin)	Oral	0.125-0.25 mg
Beta Blockers		
Metoprolol (Toprol)	Oral	50-100 mg
Atenolol (Tenormin)	Oral	50-100 mg
Propranolol (Inderal)	Oral	40-80 mg
Acebutolol (Sectral)	Oral	200-300 mg
Carvedilol (Coreg)	Oral	6.25-25 mg
Nebivolol (Bystolic)	Oral	5-40 mg
Bisoprolol (Monacor)	Oral	2.5-20 mg
Ca Channel Blockers		
Diltiazem (Cardizem)	Oral	180-240 mg
Verapamil (Calan)	Oral	180-240 mg

Patients without other heart disease receive beta or calcium channel blockers as first line rate control therapy [95]. Patients with coronary artery disease or heart failure will receive beta-blockers. Patients with ventricular hypertrophy not warranting exclusion would receive either beta- or calcium channel blockers, while patients with heart failure will receive carvedilol, bisoprolol, or metoprolol. Rate control medications may be used in combination and doses adjusted to achieve resting heart rates <80 bpm and exercise heart rates on 6 minute walk or Holter monitoring <110 bpm [28, 92]. These criteria will also be insured by clinical activity assessment in patients capable of exercise, as monitored by the patient's clinical cardiologist.

5.2.2 Drugs Approved for Maintenance of Sinus Rhythm

Drug	Administration	Minimum recommended daily dosage	Type/Level
Propafenone (Rhythmol)	Oral	450-625 mg	1C/B
Flecainide (Tambocor)	Oral	200-300 mg	1C/B
Sotalol (Betapace)	Oral	240-320 mg	Class III/ A
Dofetilide (Tikosyn)	Oral	500-1000 mcg	Class III/A
Amiodarone (Cordarone)	Oral	200-400 mg	Class III/B
Quinidine (Quinaglute/ dex)	Oral	600-900 mcg	Class I, III/B
Dronedarone (Multaq)	Oral	800 mg	Class III

At the documentation of failure of rate control using AFFIRM [28] and AF CHF [43] criteria, or if the patient has previously failed rate control by these criteria or remains symptomatic despite AV nodal blockers, rhythm control may be started using a membrane active drug in an approach consistent with the recommended Guidelines for Management of Subjects with AF [92]. Each patient will be placed on an anti-arrhythmic drug for an appropriate period and cardioverted to sinus rhythm if necessary. During the 3 month therapy initiation period, dosage adjustments can be made or the drug replaced with a different rhythm control drug. In general, patients with no other heart disease may be treated with propafenone, flecainide, sotalol or dofetilide. Patients with underlying ischemic heart disease or isolated diastolic dysfunction may/can be treated with sotalol, dofetilide, or amiodarone. Patients with underlying heart failure can be treated with dofetilide or amiodarone. Multaq (dronedarone) should not be used in patients with NYHA IV heart failure, or NYHA Class II-III heart failure with a recent decompensation requiring hospitalization or referral to a specialized heart failure clinic. Background therapy with upstream

ACE-I / ARBs, statins, fish oil, and aldosterone antagonists will also be encouraged and tracked at each follow-up.

5.2.3 Drugs for Future Consideration

It is anticipated that other rate control agents and membrane-active anti-arrhythmic drugs may become available over the course of the trial. Since a chief aim of the trial is to provide relevant, up-to-date information for guiding drug and ablative therapy for AF, these new treatment strategies will be incorporated in CABANA once approved by the CABANA Innovative Drug Therapy and Executive Committees. Drugs which have been approved by appropriate regulatory agencies outside of the United States may be used within that jurisdiction.

5.2.4 AV Nodal Ablation

Ablation of the AV conduction system may be considered as an alternate measure in patients with inadequate rate control refractory to at least 3 rate control agents or 2 membrane-active anti-arrhythmic drugs.

5.2.5 Changing Drug Therapy

During follow-up, patients may have recurrent AF, which constitutes an endpoint for the AF Recurrence secondary endpoint. Nevertheless, these patients will continue to be followed throughout the study to establish the occurrence of the primary and the secondary composite endpoints. These patients may require other drug therapy, which can be instituted during follow-up, without patient withdrawal from the trial.

5.2.6 Cross-Over to Ablative Therapy

During follow-up, drug arm patients with recurrences may be treated with additional anti-arrhythmic drugs or alternative rate control agents. Of note, most patients included to date in single center trials were treated for over one year before undergoing ablation. Thus, it is anticipated that most patients will be treated for at least 12 months in the drug therapy arm and that patients will be fully informed of this at the time of the consent process. Cross over ablative intervention is strongly discouraged. **Crossovers must be approved by the CABANA Trial Administrative Center. Before approval is granted for a patient randomized to drug therapy to be crossed over to ablation, sites will be required to provide rationale and documentation that drug therapy options have been exhausted.**

5.2.7 Compliance with Treatment Protocols /Site Performance

The success of the trial will be enhanced by careful consideration of 1) participating Site Qualification, 2) Procedure Standardization, 3) Site performance, and 4) Follow-up tracking. High standards in each of these areas will provide the greatest assurance that optimal, protocol-dictated therapy is being delivered and that patients have the best opportunity of responding to it. Each site will be required to provide documentation of expertise in the medical management of AF, including at least 2 of the following: 1) successful participation in AFFIRM, RACE, STAF, PIAF or other multi-center clinical trials; 2) medical management of at least 30 patients with AF; 3) site expertise in clinical practice, research, or quality assurance registries or databases; 4) an active AF clinic; or 5) treatment of >20 patients with sotalol, dofetilide or amiodarone. Patient compliance with medical therapy in rate control patients will be judged from achievement and maintenance of rate control targets noted in Section 5.2. Rates of sinus rhythm among rhythm control patients in the medical arm will be monitored and benchmarked against recent clinical trials including AFFIRM, AF CHF and ATHENA. Frequent phone contacts and newsletters will encourage compliance during the therapy initiation phase. These communications will then be continued regularly during the follow-up phase. Since we desire participation by a true cross section of individuals with AF, enrollment will not be based on availability of health insurance.

The IDE: G050233 approval establishes the approach of this trial as a CMS B2 therapy. As has been seen in the Pilot Study, the therapies in this trial can be billed to Medicare/3rd party payers.

5.3 Primary Catheter Ablation for AF (Ablation Therapy)

5.3.1 Pre-ablation Assessment

Pre-ablation assessment using standard practice patterns as outlined in the AF Ablation Consensus and Venice Chart Documents [50,51], will provide baseline data for safety and efficacy outcomes analyses. All patients who are randomized to ablative intervention will also undergo baseline CT or MR scanning. These studies will form the basis for comparisons of change in LA function with ablative or drug therapy.

5.3.2 Ablation Therapies

A potential limitation of any trial examining ablative intervention for AF is the number of different methodologies used for the primary curative ablation. The NHLBI Work Group on AF Ablation, the AF Ablation Consensus [50] and the Venice Chart [50] documents all agreed that pulmonary vein (PV) isolation is the starting point for AF ablation. PV isolation is therefore the minimum required ablation procedure for every patient in the trial. This may be a variation of: 1) Circular mapping catheter-guided ablation as described by Haissaguerre et al. [50, 93, 94], 2) Antral Isolation using a circular-guided approach as described by Natale et al. [95, 96], or 3) Wide area circumferential ablation [48, 97, 98]. As described in the AF Ablation Consensus Documents [50, 51], the approach in most expert ablation centers has evolved toward larger circumferential ablation outside the PVs. The selection of ablation guidance systems (circular mapping catheters, fluoroscopy, mapping systems and intracardiac ultrasound) is left to the discretion of the site PI, providing that site has performed at least 100 AF ablation cases with that approach. The acute endpoint of ablation is the isolation of all PVs.

Adjunctive procedures such as enlarging the field of ablation for the targeting of complex fractionated atrial electrograms [47], sites of apparent ganglia [99], or the use of additional linear lesions is allowed, but only after wider area or antral PV isolation. The methods for each of these are as outlined in the AF Ablation Consensus Document [50]. Each ablative approach and adjunctive measures will be carefully tracked to establish overall contribution to outcomes. Additional factors such as 1) termination of AF with ablation, 2) non-inducibility with atrial stimulation, and 3) absence of immediately recurrent AF with 10-20 mcg/min of isoproterenol, although controversial, will be tracked. Of note: ablation of the AV conduction system is not considered an alternative for primary ablative intervention.

5.3.3 Approved Ablation Devices

The specific choice of ablation catheters is left to the investigator, but must be one or more of the catheters listed below (see also Appendix B). Catheters which have been approved by appropriate regulatory agencies outside of the United States may be used within that jurisdiction.

Manufacturer	Catheter	Reference#
St. Jude Medical	Livewire TC™ XLS™	P960016
St. Jude Medical	Therapy™ Dual / Thermocouple	P040014
St. Jude Medical	Therapy Cool Path	P060019
Biosense Webster	NAVI-STAR / NAVI-STAR DS	P990025 / P010068
Biosense Webster	Celsius Braided Tip / Long Reach	P950005
Biosense Webster	NAVI-STAR Thermo-Cool	P030031
CryoCath	Freezor® / FreezorMax	P020045

Manufacturer	Catheter	Reference#
Bard	Stinger	P000020
Boston Scientific	Blazer II RF / RPM / SteeroCath /XP	P920047 / P020025
Boston Scientific	Chilli Cooled	P980003

5.3.4 Approaches for Future Consideration

Undoubtedly, primary ablative intervention for AF will evolve over the course of this trial. In order to maximize the potential for the generalizability of CABANA findings to the broader area of AF ablation, newly evolving methods or devices will be permitted, as approved by the Innovative Ablation Therapies / Executive Committees.

5.3.5 Cross-over to Drug Therapy

Patients with recurrent AF during the blanking period can be maintained on anti-arrhythmic drug therapy, although this should be discontinued by the end of the 90-day monitoring period. Subsequent AF recurrence will be considered an endpoint for the AF freedom endpoint. Those who are highly symptomatic may subsequently receive anti-arrhythmic drug therapy, but will be followed on an intention-to-treat basis as part of the ablation treatment group for primary and secondary endpoint assessments.

5.3.6 Compliance with Treatment Protocols /Site Performance

CABANA ablation sites must be pre-qualified for participation by 1) demonstration that each site has performed ≥ 100 primary AF ablations and 2) satisfactory completion of review of performance-confirming site data by the CABANA Ablation Therapies Committee including: 1) 5 prior ablation reports; 2) demonstration of an adequate prior ablation database to establish the CABANA patient's position in the site's overall series; 3) evidence of acceptable standard follow-up practices and data collection methods; 4) 5 pre and post lasso electrograms establishing acute PV isolation success; and 5) 5 prior Carto/NavX maps showing mapping proficiency. Taken together, these will provide validation of AF ablation expertise.

Site ablation performance will be tracked throughout the trial. Ablation data including ongoing acute success rates in achieving PV isolation, ablation time, fluoroscopy time, and ablation methods captured by ablation eCRFs will be tabulated by the Data Coordinating center. Outliers will be identified for special review. Exact ablation methods, complications, and compliance with the protocol will be reviewed by the DCRI monitors and a member of the Ablation Therapy Committee. Timeliness and accuracy of eCRF data entry will also be monitored.

5.4 Guidelines for Anti-thrombotic Therapy

5.4.1 Guidelines for Anticoagulation in Drug Treated Patients

Patients with risk factors for CVA or peripheral thromboembolic events at the time of enrollment, treated with rate control agents alone, will remain on active anticoagulation therapy (warfarin, dabigatran, rivaroxiban or apixaban) throughout the duration of the trial [92]. Unlike the AFFIRM trial, patients receiving rhythm control therapy will also be required to receive adequate anticoagulation (warfarin, dabigatran, rivaroxiban or apixaban) for the duration of the trial. In the use of warfarin therapy, target INRs of 2 to 3 will be required, unless higher INRs are mandated because of underlying disease.

5.4.2 Guidelines for Anticoagulation Therapy in Ablation Patients

Anticoagulation before, during, and after the ablative intervention will follow the guidelines of the AF Ablation Consensus Document [50]. Prior to the ablative intervention, patients with persistent and long-standing persistent AF should receive adequate anticoagulation (i.e. at least

one month of warfarin anticoagulation (INRs: 2-3)), or have a TEE excluding intra-atrial thrombus at the time of the intervention. During the ablative intervention, maintaining an ACT between 300 and 400 seconds is strongly recommended. Following the ablative intervention, patients will be started on IV heparin or subcutaneous injections of low molecular weight heparin beginning 4 to 6 hours after all sheaths are removed, and appropriate anticoagulation reinstated the evening of the intervention. Thereafter, low molecular weight heparin is to be maintained until anticoagulated appropriately or standard dose warfarin achieves a target INR of 2 to 3, unless the ablation was performed at a therapeutic INR in patients maintained on warfarin through the ablation. One month following the ablation, dabigatran, rivaroxiban or apixaban may be substituted for warfarin, following recently written guidelines. Three to six months after ablation, warfarin may be replaced by full dose aspirin in patients with a CHADs score ≤ 1 . This would include patients with hypertension without hypertrophy, or those < 65 years of age, providing 1) atrial size and function are normal and 2) there is no symptomatic or asymptomatic AF by standard or full-disclosure monitoring. In those patients with a CHADs score ≥ 2 , adequate anticoagulation is to be continued throughout the trial. Randomization of warfarin discontinuation is precluded by the low post-ablation stroke rates that would require at least 10,000 patients for detecting differences in stroke prevalence. Nevertheless, the characteristics, follow-up monitoring results, and long-term anticoagulation status of ablation patients will be compared to descriptively identify predictors of events and profiles of patients at high risk for warfarin discontinuation. The utility of trans-telephonic, auto-detection / full disclosure, and Holter monitoring, as a future aid in the decision to discontinue anticoagulation will also be critically examined.

5.4.3 Newer Antithrombotic Therapies

It is likely during the course of the trial that newer antithrombotic therapies non-inferior to warfarin or dabigatran will be approved. These agents may be used as replacement therapy for warfarin on approval of local regulatory agencies and the Innovative Antithrombotic Therapies/Executive Committees.

5.4.4 Items Left to the Discretion of the Physician

Specific items left to the investigators discretion include: 1) specific choice of rate control vs. rhythm control drug therapy and specific drugs to be used; 2) hospitalization to initiate anti-arrhythmic drug therapy; 3) choice of TEE guided direct current cardioversion (DCCV) vs. DCCV after 4 weeks of appropriate anticoagulation therapy, such as warfarin to an INR of 2-3; 4) pre-ablation TEE assessment in patients with simple paroxysmal AF and hypertension without hypertrophy; 5) continuation of warfarin to maintain a therapeutic INR at the time of catheter ablation; 6) selection of warfarin versus dabigatran, rivaroxiban or apixaban.

5.5 Management of Arrhythmia Recurrences During Follow-Up

During the 3 months of “therapy initiation”, patients randomized to drug therapy may receive alternative drugs. Patients in the ablation arm may undergo repeat ablation in those cases where the recurrent arrhythmia is not felt to be due to the irritation and inflammation of the ablative intervention. These patients may also be treated with rhythm control drug therapy, providing it is discontinued by the end of the blanking or “therapy initiation phase”. Any event occurring during this period will be tracked as an “Early Event”. Long-term follow-up with respect to efficacy will begin 3 months after the initiation of drug therapy or ablation therapy. These events will be used for the determination of overall freedom from recurrent AF, but will not be of sufficient importance to remove the patient from the trial. Patients achieving a secondary endpoint through non-fatal events will be followed throughout the remaining follow-up period.

6.0 Definitions & Adjudication for Study Endpoints

6.1 Primary Endpoints

The primary endpoint is the composite of total mortality, disabling stroke, serious bleeding or cardiac arrest. All components will be adjudicated by an independent Clinical Events Committee (CEC) and the most proximate cause of the event established. A Disabling Stroke will be considered present using a modification of a Rankin Stroke score [100], and will be adjudicated by a Neurologic Events Committee. Serious (or Life-threatening) bleeding will be considered present using a modification of the GUSTO bleeding Scale adapted for use in catheter ablation [101]. These events will be tracked regardless of treatment randomization. The definition for each of these events is listed in the CEC Charter. When there is disagreement between the CEC and the principal investigator, the CEC's decision will be considered final. Procedures for adjudicating events are described in the CEC Charter, which is available upon request. The CEC will also confirm whether a death is cardiac/vascular/non-cardiovascular in origin; as well as witnessed/un-witnessed; or sudden/non-sudden. Cardiac mortality will be further categorized as tachyarrhythmic, bradyarrhythmic, heart failure, or due to other cardiac causes using the events adjudication form. Hospitalization will also be tracked with specific reason for admission (heart failure, acute ischemic event, etc.) determined by the site principal investigator as reported in the eCRF.

6.2 Secondary Endpoints & Safety Endpoints

Secondary endpoint events, including total mortality and a composite of total mortality or cardiovascular hospitalization will be confirmed.

While hospitalization for any atrial fibrillation, atrial flutter or atrial tachycardia in both treatment arms will be carefully tracked and compared, it will be considered as an "AF recurrence" and counted against efficacy, not safety. Therefore, *AF recurrence and/or worsening of AF need not be reported as an adverse event.*

7.0 Adverse Events

Adverse events, defined as any undesirable medical occurrence in a clinical study patient which occurs during the course of the study and can be attributed to a device, procedure, or medications required *by a procedure, protocol, or trial* will be tracked throughout the study.

An adverse event (AE) will be considered present if 1) there are untoward signs, symptoms, illnesses, or other medical events that develop or worsen in severity during the course of the study, 2) they are clinically relevant *and* if they are clinically related to the study. Note: Disease, signs symptoms, and or laboratory abnormalities already existing at randomization are not considered adverse events unless they represent an intensity or frequency exacerbation. An adverse event designation should reflect the reason for a diagnosis or abnormal measurement. Procedures planned prior to randomization and the conditions leading to these measures are not adverse events.

An event inherent to an intervention/medication that is expected to occur for a projected duration in some or all subjects is considered unavoidable. Unavoidable adverse events will not be tracked during the trial (*examples: pain at catheter insertion sites during and after a procedure; pain at injection sites; palpitations; nausea due to anesthesia, etc.*).

The DCRI will evaluate any safety information that is spontaneously reported in the time frame specified in the protocol. For each subject, adverse events occurring after randomization must be recorded on the applicable Adverse Events page(s) in the electronic Case Report Form (eCRF). Recording should be done in a concise manner using standard, acceptable medical terms. The adverse event recorded should not be a procedure or a clinical measurement (i.e., a laboratory value or vital sign) but should reflect the reason for the procedure or the diagnosis based on the abnormal measurement. It is the responsibility of the Principal Investigator to oversee the safety of the patients enrolled in the study at his/her site. This responsibility includes careful assessment and appropriate reporting of adverse events. The primary mechanism for reporting adverse events in CABANA is for study personnel at the clinical sites to enter the relevant information and the details and description of each event using the adverse event forms that are part of the InForm electronic data capture (EDC) system being used in the trial.

Again, *AF recurrence and/or worsening of AF need not be reported as an adverse event.*

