7.1.2 Serious Adverse Event

An adverse event that warrants additional action, includes *any* untoward event that:

1. Is fatal
2. Is life-threatening
3. Requires inpatient hospitalization or prolongation of existing hospitalization >48 hours.
Exceptions- therefore not reportable:
 - a. Preplanned (prior to the study) hospital admissions unless the hospitalization is prolonged >48 hours beyond the anticipated length of stay.
 - b. Planned admissions (as part of a study – e.g. admission for drug change or titration for treatment of atrial fibrillation)
 - c. 23 hour hospitalizations OR observation.
 - d. Hospitalization for elective procedure (e.g. cardioversion).
 - e. Emergency room visits that do not result in hospitalization.
 - f. Hospitalization to titrate or optimize medical therapy to treat recurrence of atrial fibrillation.
4. Results in persistent or significant disability or incapacity.
5. Results in a congenital anomaly or birth defect.
6. Important medical events that may not result in death, be life-threatening, or require inpatient hospitalization may be considered an SAE when, based on appropriate medical judgment, they may jeopardize the patient and may require medical or surgical intervention to prevent one of the outcomes listed above.

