7.1.4 Causal Relationship to Medical or Ablative Therapy

The International Council of Harmonization (ICH) Guidelines (1995) indicate that “reasonable causal relationship” means that “there are facts [evidence] or arguments to suggest a causal relationship.” The causality assessment must be made by the investigator based on information available at the time that the adverse event eCRF is completed. The initial causality assessment may be revised as new information becomes available.

1. **Definitely related:** there is a reasonable temporal relationship to study therapy or device
 - a. follows a known response pattern (e.g., study drug, treatment or device is known to cause this AE)
 - b. there is no alternative etiology or explanation for the event
2. **Probably related:** there is a reasonable temporal relationship which
 - a. follows a suspected response pattern
 - b. no evidence for a more likely alternative etiology though could be unrelated
3. **Possibly related:** there is a reasonable temporal relationship but
 - a. equivocal evidence that the event is study related as opposed to an alternative etiology
4. **Probably not related:** there is not a reasonable temporal relationship OR
 - a. good evidence for a more likely alternative etiology
5. **Not related:** there is not a temporal relationship OR
 - a. clear and compelling evidence that the event is due to an alternative etiology

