7.2 Adverse Event Reporting

The goal is to have an adverse event reporting process that is (a) clear and simple for site investigators and study coordinators to understand and implement, (b) satisfies all regulatory reporting requirements, (c) eliminates any duplication in data collection and reporting, and (d) has a balanced focus on both the drug and ablation arms of the trial.

All related adverse events, serious and non-serious, that occur between the time of randomization and the last study-related procedure/visit will be followed until resolution, stabilization, or to trial completion. Adverse events for subjects who discontinue study participation at any time during the study should be collected/reported through at least the time of discontinuation. In addition, the required Institutional reporting structure will be followed and/or as described in this protocol.

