7.3 Serious Adverse Event Reporting

Regardless of causality, the investigator will record all serious adverse events occurring between randomization and the last study-related procedure/visit or completion of the trial into the electronic database within 24 hours of knowledge of the event. DCRI will report all unanticipated/unexpected study related serious adverse events to Mayo Clinic, NHLBI and the DSMB chair within 2 business days of receipt.

The investigator must update the eCRF SAE when important follow-up information (final diagnosis, outcome, results of specific investigations, etc.) becomes available after submission of the initial entry. Follow-up information should be entered within forty eight (48) hours of knowledge. All reportable events will be followed until resolution, stabilization, or to trial completion, whichever occurs first. In addition, the required Institutional reporting structure will be followed and/or as described in this protocol.

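### Protocol 7.0 builds attribution into the definition of an adverse event, against 7.3 and 7.1.4: unblinded judgement selects which non-serious events are compared, and whether it also filters serious events is left open

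*Protocol*

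**What the plan says.** Protocol 7.0 sets two conditions that concern cause. An adverse event is something that "occurs during the course of the study and can be attributed to a device, procedure, or medications required" by a procedure, the protocol or the trial. It is then said to be present only where the event is clinically relevant and "if they are clinically related to the study".

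Protocol 7.1 has the investigator grade all adverse events for seriousness, severity and causality. Section 7.1.2 introduces a serious event with "An adverse event that warrants additional action, includes", and continues that it covers any untoward event meeting a seriousness criterion.

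Protocol 7.1.4 gives a five-grade causality scale that ends in Probably not related and Not related. The last grade applies when there is no temporal relationship or "clear and compelling evidence that the event is due to an alternative etiology". On who judges: "The causality assessment must be made by the investigator based on information available at the time that the adverse event eCRF is completed". Protocol 4.3 describes the randomization as unblinded.

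Protocol 7.2 says: "All related adverse events, serious and non-serious, that occur between the time of randomization and the last study-related procedure/visit will be followed" until they resolve, stabilize or the trial ends. Protocol 7.3 says: "Regardless of causality, the investigator will record all serious adverse events occurring between randomization and the last study-related procedure/visit".

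Composite adverse events are a listed secondary outcome (Protocol 2.2, SAP 3.2). SAP 9.12 tabulates named major events and other serious events descriptively, and allows chi-square tests for other adverse events where appropriate. It does not say whether events judged unrelated are counted.

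**The concern.** A definition decides what reaches the database. If attribution is part of the definition, an event judged unrelated is not an adverse event, and no later analysis can recover it. In an open-label comparison of a procedure with long-term drugs, the two arms need not be judged alike. An event soon after an ablation is easily linked to it, while an event during years of rate-control treatment is easily put down to background disease. The 7.0 wording may add to this, because it ties attribution to treatment that is required. Ablation plainly qualifies, but Protocol 5.4.4 leaves the choice of drugs to the physician, so whether a given drug was required can be argued.

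At stake is the safety comparison. Protocol 2.2.7 expects similar rates of serious adverse events in the two arms. That expectation can be checked only if all sites use the same entry rule. On-site monitoring would not reliably find omissions, since Protocol 11.1 limits visits to a subset of sites and reviews only selected serious events.

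**Working it through.** No figure in the documents bears on this point, so there is nothing to reproduce. The check is a comparison of the text, followed by two illustrations on assumed rates.

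**Non-serious events.** Section 7.0 requires attribution and relatedness. Section 7.3 does not reach these events, and nothing else in Section 7 overrides 7.0. A non-serious event judged unrelated is therefore not recorded, and cannot enter the SAP 9.12 tables or tests. Here the filter follows directly from the text.

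**Serious events.** Two readings are possible.
- Definition applied before the reporting rule: 7.1 grades seriousness among adverse events and 7.1.2 opens by calling a serious event an adverse event. An unrelated serious event then fails 7.0 and is never graded.
- Reporting rule governs: 7.1.2 goes on to any untoward event, and 7.3 sets causality aside. Section 7.3 also forwards to the DSMB chair only those unexpected serious events that are study related, which presupposes that unrelated ones are on file.

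The lower grades in 7.1.4 make sense on the second reading. At entry they have no place under 7.0 as written.

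**Illustration for serious events.** Assume equal true risk in both arms, 25% of ablation-arm and 15% of drug-arm serious events judged attributable, and a share *p* of sites (taken as the same share of events in each arm) applying 7.0 before 7.3. The remaining sites record everything.

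Recorded ratio = (0.25*p* + 1 − *p*) / (0.15*p* + 1 − *p*)

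- *p* = 0.1: 0.925 / 0.915 = 1.01
- *p* = 0.5: 0.625 / 0.575 = 1.09
- *p* = 1: 0.25 / 0.15 = 1.67

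With 20% and 10% instead, the three ratios are 0.92/0.91 = 1.01, 0.60/0.55 = 1.09 and 0.20/0.10 = 2.00.

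**Illustration for non-serious events.** SAP section 2 material gives 2,204 subjects at 1:1, so about 1,102 per arm. Assume equal true incidence and attribution of 70% in one arm and 50% in the other. The recorded risk ratio is 0.70/0.50 = 1.40. The chance of a two-sided p < 0.05 is approximately Φ(|p₁ − p₂| / √{[p₁(1 − p₁) + p₂(1 − p₂)]/1,102} − 1.96), where p₁ and p₂ are the recorded proportions:

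- true incidence 5% (3.5% v 2.5% recorded): 0.28
- 10% (7% v 5%): 0.51
- 20% (14% v 10%): 0.82
- 30% (21% v 15%): 0.96

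With 60% v 50% attribution the ratio is 1.20 and the chances are 0.11, 0.18, 0.32 and 0.47. With equal attribution the chance stays at 0.05.

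**The case against.** The case on the other side is strong for serious events. A specific instruction normally governs a general definition, and 7.3 is specific. Section 7.4 lists serious, related and unanticipated as separate conditions, which fits a database holding unrelated serious events. The 7.2 sentence on related events governs follow-up, so it is not evidence of a filter on recording. The causality grade may be revised after entry, so even a related-only system would have some use for the lower grades. All of this stands.

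The gravest harms also have other routes. Death, stroke, bleeding and cardiac arrest have their own event forms (Protocol 9.2, SAP 6), and SAP 8 describes blinded adjudication. Hospitalizations are tracked with a reason for admission (Protocol 6.1), and the DSMB sees endpoint data as well as safety data. SAP 9.12 plans no overall ratio of serious events. Several of its named categories, such as drug-related pro-arrhythmia and amiodarone toxicity, need attribution simply to be classified. This stands too.

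It may also be said that recording all serious events but only related non-serious ones is a reasonable way to limit collection. It can be, but the documents do not state it as a choice, and 7.0 makes no exception for serious events.

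A reader might infer that attribution decides which serious events enter the arm comparison, and that a ratio near 1.67 should be expected. The documents do not support that. It would need every site to disregard 7.3, on attribution rates and a direction that appear nowhere in them.

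**Conclusion.** Sections 7.0, 7.1.2, 7.1.4 and 7.3 conflict as written and must be reconciled. For non-serious events the consequence follows from the text: an unblinded investigator's view of cause decides what is recorded, so the planned tables and tests compare attributed events, not occurrences. For serious events the weight of the text favours full recording, but a literal reading of 7.0 remains available to a site, and neither 7.1 nor 7.1.2 closes it. The primary comparison is untouched.

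The size is unknown. The ratios shown rest on assumed attribution rates, an assumed direction and equal true risk. For serious events they stay between 1.01 and 1.09 unless more than half of sites apply 7.0 before 7.3. The point should be acted on because the correction is cheap and removes a doubt about the safety data that the analysis itself cannot resolve.

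**What to change.** - **Protocol 7.0:** remove attribution and relatedness from the definition for serious events, so that it agrees with 7.3 and causality is graded only under 7.1.4. The related-only rule may stay for non-serious events if it is stated as a deliberate choice.
- **SAP 9.12:** state that serious adverse events are tabulated by arm regardless of causality, with related ones in a second table. Label the non-serious tables and chi-square tests as covering investigator-attributed events only, to be read with the possible unblinded-attribution bias in mind.
- **Sites:** send a clarification letter and query for unrelated serious events that were left out.

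The cost is a protocol clarification, a few sentences in the SAP and some retrospective site queries. No data are asked for beyond what 7.3 already requires. The SAP still speaks of follow-up in the future tense, so the queries look feasible.
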